2.7 Safety analyses

All safety analyses will be based on the All-Treated subjects (ATS) population.

2.7.1 Adverse events (AEs)

Adverse events (AEs) will be graded according to the CTCAE, Version 4.0. Adverse events will be coded using the Medical Dictionary for Regulatory Activities (MedDRA). For the final analysis, version 24.1 of MedDRA will be used.

All AEs will be summarized based on frequency and proportion of total subjects experiencing the event, grouped by system organ class and preferred term (PT).

A summary of number and percentage of subjects with any adverse events by maximum grade will be produced for each histologic cohort. In this summary AEs will be sorted by PT in descending order of total incidence. The summary will use the following algorithms for counting the subject:

Preferred term row: Subjects experiencing the same AE preferred term several times with different grades will only be counted once with the maximum grade.

Any event row: Each subject with at least one adverse event will be counted only once at the maximum grade no matter how many events they have.

For the legal requirements of ClinicalTrials.gov and EudraCT, two required tables of on-therapy adverse events which are not serious adverse events with an incidence of at least 5% and on-therapy serious adverse events and SAEs suspected to be related to study treatment will be provided by system organ class and preferred term for the all treated subjects population.

If for the same patient, several consecutive AEs (irrespective of study treatment causality, seriousness and severity) occurred with the same SOC and PT:

- a single occurrence will be counted if there is ≤ 1 day gap between the end date of the preceding AE and the start date of the consecutive AE
- more than one occurrence will be counted if there is > 1 day gap between the end date of the preceding AE and the start date of the consecutive AE

For occurrence, the presence of at least one SAE / SAE suspected to be related to study treatment / non SAE has to be checked in a block e.g., among AEs in a ≤ 1 day gap block, if at least one SAE is occurring, then one occurrence is calculated for that SAE.

The number of deaths resulting from SAEs suspected to be related to study treatment and SAEs irrespective of study treatment relationship will be provided by SOC and PT.

All SAEs and fatal SAEs will be tabulated based on the number and percentage of subjects who experienced the event. The summary tables will be displayed in descending order of total incidence by PT only.

Separate listings with subject-level details will be generated for fatal SAEs and non-fatal SAEs. These listings will include PT, verbatim text, onset date, data of resolution, outcome, event duration, time since first and last dose, maximum grades, seriousness, action taken with study treatment and relatedness to study treatment.

The following categories of AEs will be summarized in descending order of total incidence by PT only:

- AEs Leading to Permanent Discontinuation of Any Study Treatment
- AEs Leading to Dose Interruptions
- AEs Leadings to Dose Reductions.

2.7.1.1 Adverse events of special interest / grouping of AEs

A comprehensive list of MedDRA terms based on the program-level electronic case retrieval sheet (eCRS) will be used to identify each type of events. Changes to the MedDRA dictionary

may occur between the start of the study and the time of reporting and/or emerging data from on-going studies may highlight additional adverse events of special interest, therefore the list of terms to be used for each event of interest and the specific events of interest will be based on the safety management team (SMT) agreements in place at the time of reporting.

Adverse events of special interest include:

- Skin related toxicities
- Ocular events
- Cardiac related events
- Hepatic disorders
- Pneumonitis/Interstitial lung disease
- Bleeding events
- Hypertension
- Hypersensitivity
- New primary or secondary malignancy
- Venous thromboembolism
- Pyrexia
- Uveitis
- Pre-renal and Intrinsic Renal Failure
- Pancreatitis
- Hyperglycemia
- Neutropenia

The summary of number and percentage of subjects with each type of adverse event of special interest by maximum grade will be produced for each histologic cohort and all cohorts combined. AEs will be sorted by PT in descending order of total incidence.

2.7.2 Deaths

All deaths will be summarized based on the number and percentage of subjects, by time of death (on-therapy and post-therapy) and the primary cause of death. On-therapy and post-therapy are defined in section 2.1.1. A supportive listing will be generated to provide subject-specific details for subject who died.

2.7.3 Laboratory data

The full list of laboratory tests is given in the study protocol section 7.4.8.

Laboratory grades will be reported using the Common Terminology Criteria for Adverse Events (CTCAE v4.0).

Summaries of worst case grade increase from baseline grade will be provided for all the lab tests that are gradable by CTCAE v4.0. These summaries will display the number and percentage of subjects with a maximum on-therapy grade increasing from their baseline grade. Any increase in grade from baseline will be summarized along with any increase to a maximum grade of 3 and any increase to a maximum grade of 4. Missing baseline grade will be assumed as grade 0. In addition, the summary will include grade increase from baseline by scheduled

visits. For laboratory tests that are graded for both low and high values, summaries will be done separately and labeled by direction, e.g., sodium will be summarized as hyponatremia and hypernatremia.

For lab tests that are not gradable by CTCAE v4.0, summaries of worst case changes from baseline with respect to normal range will be generated. Decreases to low, changes to normal or no changes from baseline, and increases to high will be summarized at each scheduled visit as well as for the worst case on-therapy. If a subject has a decrease to low and an increase to high during the same time interval, then the subject is counted in both the “Decrease to Low” categories and the “Increase to High” categories. Detailed derivation of baseline assessment is specified in Section 2.1.1.

Unless otherwise specified, the denominator in percentage calculation at each scheduled visit will be based on the number of subjects with non-missing value at each particular visit.

An eDISH plot showing the peak on-therapy total bilirubin versus peak on-therapy ALT will be plotted by histological cohort combining primary analysis and expansion cohorts. Upon data review during the conduct of the study, an additional eDISH plot might be considered showing peak on-therapy total bilirubin versus peak on-therapy AST if there are potential cases based on AST rather than ALT. Subject plots showing the time course of ALT, AST, ALP and total bilirubin will also be produced. The number and percentage of subjects with ALT, AST and bilirubin above relevant thresholds (e.g. 3 x ULN) at any time on-therapy will be displayed. Criteria relating to the combined elevations of ALT or AST and bilirubin are based on the peak values at any time on-therapy and do not have to be concurrent.

2.7.4 Other safety data

2.7.4.1 ECG and cardiac imaging data

The results of scheduled assessments of ECG will be summarized. A summary of ECG findings will classify each result into “Normal”, “Abnormal, not clinically significant” or “Abnormal, clinically significant” as entered on the eCRF. Bazett’s and Fridericia’s corrections of QT values will be summarized using the categories in section 4.7 for both an increase in grade from baseline and the amount of increase. The summaries will display results by visit and for the worst case (largest increase) post-baseline.

2.7.4.2 Vital signs

Systolic and diastolic blood pressure, heart rate, temperature in degrees Celsius will be summarized by histologic cohort and visit. The worst case post baseline will display the largest value after baseline in the study. Changes from baseline in systolic and diastolic blood pressure, heart rate and temperature in degrees Celsius will be summarized including the categories in section 4.10.

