g. All events of possible treatment-induced liver injury with hyperbilirubinemia defined as:

- ALT ≥ 5 times ULN and bilirubin ≥ 3 times ULN (>35% direct) or ALT ≥ 5 times ULN and INR >1.5, if INR is measured, with no existing liver disease
OR
- ALT ≥ 8 times ULN **and** bilirubin ≥ 5 times ULN (>35% direct) or INR >1.5, if INR is measured, with pre-existing liver disease

NOTE: INR measurement is not required and the threshold value stated will not apply to subjects receiving anticoagulants.

NOTE: Bilirubin fractionation is performed if testing is available. If testing is unavailable, record presence of detectable urinary bilirubin on dipstick indicating direct bilirubin elevations and suggesting liver injury. If testing is unavailable and a subject meets the criterion of total bilirubin ≥ 3 times ULN, if no existing liver disease or ≥ 3 times ULN if pre-existing liver disease; the event is still reported as an SAE. If INR is obtained, include values on the SAE form. Elevations in INR >1.5 suggest severe liver injury.

h. Protocol-specific SAEs:

- cuSCC (Section 8.2.2.1), new primary melanomas (Section 8.2.2.2) and **non-cutaneous malignancies (Section 8.2.2.3)** with the exception of basal cell carcinoma (BCC). BCC should be reported as an AE or SAE based on the discretion of the investigator.
- LVEF that meets the dose interruption criteria (Section 8.1.1.2): absolute LVEF decreases of $>10\%$ from baseline (not relative decrease) and below the LLN
- Liver chemistry events of ALT $\geq 3 \times$ ULN **and** bilirubin $\geq 2 \times$ ULN ($>35\%$ direct bilirubin) or ALT $\geq 3 \times$ ULN **and** INR >1.5 , if INR measured which may indicate severe liver injury (possible ‘Hy’s Law’) (Section 8.1.3.1)
- RPED also referred to as central serous retinopathy (CSR) or RVO (Section 8.2.7)
- Pyrexia accompanied by hypotension or dehydration requiring IV fluids or renal insufficiency or severe rigors/chills in the absence of an obvious infectious cause (Section 8.2.3).

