4.5 Multiple Assessments

All data will be reported according to the nominal visit date for which it was reported (that is, no visit windows will be applied during dataset creation). Unscheduled data will only be included in the display sections that report worst-case on-therapy.

If multiple assessments are reported on the same date for the same scheduled planned time, then the mean of multiple measurements reported for the same date will be analyzed, with the exception of laboratory data reported from both central and local laboratories. If laboratory data is reported from both central and local laboratories with the same date, then the central laboratory data will be analyzed to provide consistency with measurements from other subjects.

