4.10 Vital signs

To identify heart rate values of potential clinical importance, NCI-CTCAE v4.0 will be used to assign categories that align with the grades for ‘Sinus bradycardia’, ‘Sinus tachycardia’, ‘Supraventricular tachycardia’, and ‘Ventricular tachycardia’.

The following criteria will be used to flag heart rate values that are values of potential clinical importance:

Vital Sign Parameter	Potential Clinical Importance (PCI) Range	Unit
Decrease from baseline Heart Rate	Decrease to <60	bpm
Increase from baseline Heart Rate	Increase to >100	bpm

To identify blood pressure values of potential clinical importance, NCI-CTCAE v4.0 will be used to assign categories that align with the grades for 'Hypertension'.

Vital Sign Parameter	Potential Clinical Importance (PCI) Range	Unit
Increase from baseline Systolic Blood Pressure	≥120 to <140 (Grade 1) ≥140 to <160 (Grade 2) ≥160 (Grade 3)	mmHg
Increase from baseline Diastolic Blood Pressure	≥80 to <90 (Grade 1) ≥90 to <100 (Grade 2) ≥100 (Grade 3)	mmHg

To identify temperature values of potential clinical importance, NCI-CTCAE v4.0 will be used to assign categories that align with the grades for 'Hypothermia' and 'Fever'.

Vital Sign Parameter	Potential Clinical Importance (PCI) Range	Unit
Increase from baseline temperature	Increase to ≥38	Degrees C
Decrease from baseline Diastolic Blood Pressure	Decrease to ≤35	Degrees C

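### SAP 2.7.4.2 takes the largest post-baseline value as the worst case for every vital sign, so the worst-case display misses most of the low heart rates and temperatures that SAP 4.10 classes as potentially important

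*SAP*

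**What the plan says.** SAP 2.7.4.2 has three parts.

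- Values: "Systolic and diastolic blood pressure, heart rate, temperature in degrees Celsius will be summarized by histologic cohort and visit".
- Worst case: "The worst case post baseline will display the largest value after baseline in the study". No parameter is excepted.
- Change from baseline: blood pressure, "heart rate and temperature in degrees Celsius will be summarized including the categories in section 4.10".

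SAP 4.10 then sets the ranges.

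- Heart rate runs both ways: "Decrease to <60" and "Increase to >100" bpm, tied to CTCAE terms for bradycardia and tachycardia.
- Temperature runs both ways: a rise to 38 °C or more, and a fall to 35 °C or less. The row for the fall is labelled "Decrease from baseline Diastolic Blood Pressure", although its unit is degrees Celsius and the lead-in names hypothermia and fever.
- Blood pressure has increases only, aligned to hypertension grades.

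On unscheduled readings, SAP 4.5 says: "Unscheduled data will only be included in the display sections that report worst-case on-therapy". SAP 2.1 keeps unscheduled visits out of summaries except for deriving minima and maxima, and presents them in listings. Protocol 18.3.3.1.3 confines the vital-sign summaries to scheduled assessments and has all data listed.

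**The concern.** A maximum is the wrong statistic for a fall. The SAP names two low ranges as potentially important and then defines the worst case so that a low reading is overwritten by any normal reading from the same subject.

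This looks like an oversight, because direction is handled properly elsewhere. SAP 2.7.3 counts a subject under both decrease and increase when laboratory values move both ways. SAP 2.7.4.1 uses the largest increase for QTc, which fits because the QTc ranges in 4.7 all run upward. SAP 2.1 foresees minima, but no section assigns one to vital signs.

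Unscheduled readings are where this bites most. Protocol 7.4.4 allows extra vital signs when the subject's condition calls for them, and the worst-case display is the only summary open to such readings.

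Change in vital signs is part of the secondary safety endpoint. Low blood pressure also has a place in this trial's safety profile, since one protocol-specific SAE is "Pyrexia accompanied by hypotension or dehydration requiring IV fluids or renal insufficiency" (protocol 11.2).

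**Working it through.** The plan states no figure to reproduce. The check is a reading of the rules, followed by an illustration.

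**1. The rule on constructed values** (invented to test the logic)

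| Parameter | Post-baseline readings | Worst case as written (maximum) | Minimum |
|---|---|---|---|
| Heart rate, bpm | 72, 55, 80 | 80 | 55 |
| Temperature, °C | 36.6, 34.9, 37.0 | 37.0 | 34.9 |
| Systolic pressure, mmHg | 120, 82, 118 | 120 | 82 |

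The readings of 55 and 34.9 fall in the low ranges of SAP 4.10, and neither reaches the worst case. The exception is a subject with every reading low: heart rates of 58, 55 and 57 have a maximum of 58, which is still below 60.

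**2. Where a low reading can be seen**

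| Reading taken at | By-visit and category summaries | Worst-case display as written | Listings |
|---|---|---|---|
| Scheduled visit | Yes (SAP 2.7.4.2, 4.10) | Only if all readings are low | Yes |
| Unscheduled visit | No (SAP 2.1, 4.5) | Only if all readings are low | Yes |

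This treats the post-baseline worst case of 2.7.4.2 as one of the on-therapy worst-case displays meant in 4.5. SAP 2.1 supports that, since it covers both post-baseline and on-treatment extremes.

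**3. Illustration of size**

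Assumptions, not document figures: k post-baseline readings per subject, each low with probability p, independent of one another.

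- P(at least one low reading) = 1 − (1 − p)^k
- P(the largest reading is itself low) = p^k

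| k | p | At least one low | Maximum is low |
|---|---|---|---|
| 3 | 0.05 | 1 − 0.95³ = 14.3% | 0.05³ = 0.0125% |
| 3 | 0.20 | 1 − 0.80³ = 48.8% | 0.20³ = 0.8% |
| 6 | 0.05 | 1 − 0.95⁶ = 26.5% | 0.05⁶ = 0.0000016% |
| 6 | 0.20 | 1 − 0.80⁶ = 73.8% | 0.20⁶ = 0.0064% |

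**4. What independence does to these figures**

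Readings within a person are correlated. At the other extreme, where a subject's readings are all low or none are, both probabilities equal p and nothing is lost. Real data lie between. The direction of the error is certain; its size is not.

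**The case against.** The strongest reply is that SAP 2.7.4.2 does not say the decrease categories are filled from the maximum. The sentence that calls on 4.10 concerns change from baseline and is separate from the worst-case sentence, and the heart-rate and temperature categories are worded by direction. A programmer could derive them by direction, in line with the minima foreseen in SAP 2.1. This is fair as far as it goes. But the only worst-case rule written for vital signs is the maximum, and nothing assigns a minimum to them.

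The second reply is that safety information is not lost, and this largely stands. Low values at scheduled visits can appear in the by-visit category summaries. Protocol 11.3 has clinically significant abnormalities, and those leading to intervention, recorded as AEs or SAEs, and SAP 2.7.1 tabulates them. Pyrexia and renal failure are events of special interest in SAP 2.7.1.1. Pyrexia with hypotension reaches the SAE tables whatever the vital-sign table shows. What remains is that by-visit counts do not give the number of subjects who were ever low, and unscheduled lows do not enter them.

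Third, protocol 18.3.3.1.3 limits vital-sign summaries to scheduled assessments, so omitting unscheduled readings could be called compliance. However, SAP 2.1 and 4.5 already admit them to extremes, so the two documents need reconciling in any case.

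Fourth, the missing hypotension category is not caused by the maximum rule. The blood pressure ranges are aligned to hypertension, and neither document gives a numerical cutoff for low pressure. This stands.

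**Conclusion.** The worst-case rule in SAP 2.7.4.2 does not match the ranges in SAP 4.10. As written, the worst-case display shows a low heart rate or temperature only for a subject with no post-baseline reading above the low range, and an unscheduled low is otherwise left to the listings. With three to six independent readings at 5% to 20% low, 14% to 74% of subjects would have at least one low reading, against at most 0.8% with a low maximum. Those inputs are assumed, and correlation within subjects would narrow the gap.

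Four stronger readings are tempting and not supported.

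- That low values can never be a worst case: a subject who is low throughout is still shown.
- That low values vanish from every summary: scheduled lows remain available to the by-visit categories, and clinical events to the AE and SAE tables.
- That the plan is obliged to categorise hypotension: the documents set no threshold, and the SAE definition supports event capture, not a blood-pressure cutoff.
- That the mislabelled row would flag diastolic pressure: its unit and lead-in show temperature is meant, so this is a clerical error.

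The matter is a descriptive safety display. Response rate, the time-to-event endpoints, the decision rules and error rates are unaffected.

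**What to change.** In SAP 2.7.4.2, define worst case by direction: the largest post-baseline value for the increase categories and the smallest for the decrease categories. Include unscheduled readings in both, as SAP 2.1 and 4.5 allow, and let a subject count in both directions as in SAP 2.7.3. Because protocol 18.3.3.1.3 restricts these summaries to scheduled assessments, state which rule governs and record any departure from the protocol; SAP section 3 at present declares no changes.

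In SAP 4.10, relabel the row for a fall to 35 °C or below as temperature.

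Displaying the minimum systolic and diastolic values would show low blood pressure without a new threshold. A hypotension category is optional.

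The cost is SAP wording, one derived minimum per parameter and a somewhat longer table. No new data are needed.

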2.8 Pharmacokinetic endpoints

Summary statistics of concentration-time data for trametinib, dabrafenib and metabolites of dabrafenib (Hydroxy-dabrafenib and Desmethyl-dabrafenib) will be provided, both for the full PK population and separately for subjects from Japanese and non-Japanese race categories. Concentration-time data for trametinib, dabrafenib and its metabolites will be listed.

2.12 Interim analysis

Interim analyses have been carried out to monitor efficacy and safety at regular intervals through the study enrollment and for health authority submission and publication after the end of enrollment. Details of interim analyses are given in section 18.3.2 of the protocol and the interim reporting and analysis plans.

3 Change to protocol specified analyses

No changes were made to analyses specified in the protocol.

4 Appendix

4.1 Clinical review of anti-cancer therapies for censoring criteria

Due to the inconsistent recording of anti-cancer therapies (including surgeries) in the eCRF, a manual review of all relevant therapies will be carried out to ensure that the correct records are used to censor the best confirmed overall response, progression-free survival and duration of response. Specifically, spreadsheets of unique on-therapy or follow-up anti-cancer therapies, radiotherapies, and cancer-related surgeries will be sent to a clinical reviewer to identify the interventional treatments for the disease under study and distinguish them from diagnostic procedures, such as biopsies, and surgeries for adverse events not connected with the disease under study, such as squamous cell carcinoma.

4.2 Extended Loss to Follow-up or Extended Time without an Adequate Assessment

Since missing scheduled disease assessments prior to progression or death increases the uncertainty about when the event actually occurs, PFS and DoR will be censored for subjects who have progression or die after missing two or more scheduled disease assessments. Specifically, if there are two or more scheduled assessments which are missing followed by progression or death, PFS and DoR will be censored at the last adequate assessment prior to progression or death.

For the purpose of this calculation, the last adequate assessment is defined as the last assessment prior to progression or death with response other than NE or missing.

For solid tumor cohorts (ATC, BTC, GIST, NSGCT/NGGCT, ASI, WHO Grade 1 or 2 Glioma and Grade 3 or 4 Glioma) and MM cohort, when the scheduled disease assessment is every 8 weeks (for the first 48 weeks of study treatment), a window of 119 days (16 weeks + 7 day window) will be used to determine whether there was an extended time without adequate assessment. When the scheduled disease assessment is every 12 weeks (after the first 48 weeks of study treatment), a window of 175 days (24 weeks + 7 day window) will be used to determine whether there was an extended time without adequate assessment. Specifically, extended lost-to-follow-up period is defined using different time windows as described in [Table 4-1](#).

Table 4-1 Extended lost-to-follow-up period at different study times

Last adequate assessment	Extended lost-to-follow-up period
<= end of week 44	16 + 1 weeks (119 days)

Last adequate assessment	Extended lost-to-follow-up period
(<=308 days)	
>= beginning of week 45 – <= end of week 54 (>308 days, <=378 days)	20 + 1 weeks (147 days)
>= beginning of week 55 (>378 days)	24 + 1 weeks (175 days)

For the HCL cohort, the scheduled disease assessment is every 4 weeks for the first 48 weeks of study treatment, then at least every 8 weeks for patients tolerating the study drug in the judgement of the treating investigator. Following protocol amendment 11, the interval between assessments beyond the first 48 weeks is increased to at least every 12 weeks. To provide reasonable allowance for missed assessments within the new schedule, the same rules will be used for HCL as for the solid tumor cohorts and MM to determine whether there was an extended time without adequate assessment.

